9.6.2 Analysis Plan for PRO Endpoints

PROs endpoints will be analyzed at the final analysis time for the primary endpoint. Any participants who take the PROs surveys at more than 1 time-point will be eligible for analysis. The primary endpoint for HRQL is FBSI TSE subscale score at 6 and 15 months after the start of chemotherapy. The primary endpoint of ovarian function is rate of amenorrhea at 15 months. Amenorrhea is defined as the absence of menses without secondary reason (e.g., pregnancy, oophorectomy or receipt of LHRH agonist, etc.) for the whole 6 months prior to the 15-month survey (i.e., no menses between 9 and 15 months). The primary analysis of HRQL will be assessed in all eligible patients. The primary analysis of rate of amenorrhea will be assessed in women aged 18-49 at enrollment who are premenopausal at cancer diagnosis.

Subscale scores for HRQL endpoint will be prorated by multiplying the sum of the subscale by the number of items in the subscale, then dividing by the number of items actually answered: Prorated subscale score = (sum of items cores) * (number of items in subscale) / (number of items answered). When there are missing data, prorating by subscale in this way is acceptable as long as more than 50% of the items are answered in each subscale. Standard descriptive and graphical analyses will be used initially to examine missing data patterns, and to understand the relationship between variables for HRQL scores. The assessment scores for the HRQL will be compared between the two treatment arms at all time points, using two samples t test (or Wilcoxon rank sum test if the distribution of the score is not symmetric). Change in the HRQL scores between all other time points and the baseline visits will be compared between the two arms using two sample t tests. Similar analyses will be conducted for each NCCT-FACT FBSI subscales. The mean score and proportion of moderate/severe symptoms will be compared between treatment arms for each individual FBSI item at 6 months after the start of chemotherapy using Wilcoxon rank sum test and Fisher exact test, respectively, as an exploratory analysis. Mixed effect models will be constructed as another exploratory analysis to estimate the time profile of HRQL in the two treatment arms and to evaluate treatment-by-time interactions. Time will be included as a continuous variable if there is a linear trend in HRQL over time or a set of dummy variables if non-linear trend exists for HRQL. Likelihood ratio test will be used for model selection. Adjusted covariates in the mixed effect models will include patient demographic and disease characteristics, such as age, ECOG PS, clinical stage at diagnosis, residual cancer burden, prior therapy, et al.

Fisher exact test will be used to examine the difference in rates of amenorrhea between the arms at 15 months. Logistic models will be used for regression analysis for amenorrhea. Adjusted covariates in the logistic models will include patient demographic and disease characteristics, such as age, ECOG PS, clinical stage at diagnosis, residual cancer burden, prior therapy, et al.

In all analyses, P-values will be two-sided. A level of 2.0% will be considered statistically significant for HRQL comparison at 6 months after the start of chemotherapy between two arms. A level of 3.0% will be considered statistically significant for HRQL comparison at 15 months after the start of chemotherapy between two arms. For all other analysis, a level of 5% will be considered statistically significant. No adjustment will be made for multiple comparisons for secondary and exploratory endpoints.

For neurotoxicity (platinum arm) and adherence (capecitabine arm), it will be descriptive only. Neurotoxicity is measured by the FACT-GOG/NTx 11-item subscale score at each time point. The FACT-GOG/NTx subscale score is calculated in a similar way as that for HRQL endpoint. Mixed effect model will be constructed as an exploratory analysis to estimate the time profile of neurotoxicity in the platinum arm. For adherence for capecitabine, the distribution of the

adherence score will be displayed via box-and-whisker plot. The proportion of high, medium and low adherence will be calculated along with the binomial exact 95% confidence interval. The adherence score for each cycle will be calculated. The reasons for non-adherence will be summarized.

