9.6 PRO Study

The study will assess the difference in health-related quality of life (HRQL) between two chemotherapy arms and to describe the rate of neurotoxicity over time in the platinum arm, the rate of medication adherence in the capecitabine arm and the rates of amenorrhea in both arms.

All participants enrolled on the main study are potentially eligible for the PRO assessments after its activation in addendum #4. Patients (regardless of molecular subtype) will be enrolled consecutively for the PRO study until reaching the target sample size for the PRO primary endpoint (i.e., 362 patients with baseline PROs assessments, see Section [9.5.1](#)). PROs assessment for HRQL, neurotoxicity or ovarian function will not be administered in the rest of the patients enrolled for the assessment of the clinical outcomes. The adherence measure (Medication Adherence Scale) for capecitabine will be descriptive and administered to all patients in this cohort.

Rev. Add#5

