HRQL will be measured by the FBSI Treatment Side Effects (TSE) subscale score in the study, an aggregate score of 4 items from the NCCN-FACT FBSI-16 scale. Higher score represents better HRQL (score range 0-16). Based on Garcia's study (Value in Health 2012), the minimally important difference (MID) for the FBSI-TSE is 1.5 points, and the standard deviation (SD) for the score is about 3.7. A total of 326 patients will be needed to provide a 90% power to detect an effect size (i.e., MID/SD) of 0.4 at 6-months post baseline, using two-sample t test with one-sided type I error rate of 0.01. For HRQL comparison at 15 months, 290 patients would be needed for this test with one-sided type I error rate of 0.015 and 90% power. Assuming an overall attrition rate of approximately 12% by 6 months after the start of chemotherapy and 20% by 15 months after the start of chemotherapy for the PROs assessment in both arms, it is expected that about 362 patients will be needed for the primary analysis for HRQL in the study to provide the 326 patients for the HRQL test at 6 months after the start of chemotherapy and the 290 patients for HRQL test at 15 months after the start of chemotherapy.

Rev. 9/17
Rev. Add#5

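### Possible improvement: the two powered quality-of-life tests (FBSI-TSE at 6 and 15 months) could be adjusted for the baseline score already collected

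*Combined protocol and SAP*

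**What the plan says.** Section 9.6.2 defines the endpoint: "The primary endpoint for HRQL is FBSI TSE subscale score at 6 and 15 months after the start of chemotherapy". It is the score itself, not the change from baseline. The test is also in 9.6.2: "The assessment scores for the HRQL will be compared between the two treatment arms at all time points, using two samples t test", with the Wilcoxon rank sum test if the distribution is not symmetric. Section 9.6.1 sizes the 6-month comparison the same way, "using two-sample t test with one-sided type I error rate of 0.01", and the 15-month comparison at one-sided 0.015. Section 9.6.2 restates these as two-sided levels, for example "A level of 2.0% will be considered statistically significant for HRQL comparison at 6 months", and 3% at 15 months. That sentence does not say whether score or change is meant, but the sizing and the endpoint definition point to the score.

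The FBSI is collected at baseline in both arms (sections 5.5 and 7.1), and section 9.6 counts the recruitment target as "362 patients with baseline PROs assessments". The plan uses the baseline score in two other analyses, neither of which has its own sample size:

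- Change scores: "Change in the HRQL scores between all other time points and the baseline visits will be compared between the two arms", again by t-test.
- Exploratory mixed models, where baseline may enter as one of the responses. On covariates the text says: "Adjusted covariates in the mixed effect models will include patient demographic and disease characteristics". The examples that follow form an open list, which does not name a baseline quality-of-life score.

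The analysis set is wider than the recruitment target: "Any participants who take the PROs surveys at more than 1 time-point will be eligible for analysis". On that wording a patient without a baseline score could be analysed.

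**The concern.** In an unadjusted comparison of follow-up scores, whatever part of the between-patient variation the baseline score predicts stays in the error term, and a chance difference between arms at baseline is not corrected. Here the baseline is already collected at no further cost, and these are the only powered quality-of-life tests in the trial. Section 1.8 says their results will matter for counselling patients whether platinum proves superior or only non-inferior. A model that uses the baseline score could be specified before the analysis, which takes place with the final IDFS analysis.

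The change-score tests do not fill this gap. They carry no allocated error rate, and at modest correlations they are less powerful than the unadjusted test (see the table below).

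**Working it through.** **Inputs.** From section 9.6.1: minimally important difference 1.5 points, SD of the score 3.7, effect size 0.4, power 90%, one-sided alpha 0.01 (6 months) and 0.015 (15 months), attrition 12% and 20%. From section 9.6: 362 patients with a baseline assessment. From section 9.2: 1:1 allocation. Assumed, because the documents do not give it: the correlation rho between baseline and follow-up FBSI-TSE, taken as equal at both visits.

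**1. The plan's own figures.** Total N = 4(z₁₋α + z₀.₉)² / d².

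- 6 months, d = 0.4: 4(2.326 + 1.282)² / 0.16 = 325.4, so 326 in two equal arms, as stated.
- 15 months, d = 1.5/3.7 = 0.405: 290, as stated. With d = 0.4 the formula gives 298.

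Both figures reproduce without any adjustment for baseline, so the sizing and the planned test agree.

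**2. Patients available.** 362 × 0.88 = 318.6 at 6 months and 362 × 0.80 = 289.6 at 15 months, taken as 318 and 290.

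**3. Unadjusted power** (noncentral t, N − 2 degrees of freedom, noncentrality d√(N/4)). With d = 0.4: 89.0% at 318 and 88.9% at 290. With the stated 326 at 6 months: 89.8%. With d = 1.5/3.7: 89.8% at 318 and 89.8% at 290. The plan meets its 90% target within rounding.

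**4. ANCOVA on baseline.** The residual variance is multiplied by 1 − rho², so d is replaced by d/√(1 − rho²), with N − 3 degrees of freedom. For the change score the variance factor is 2(1 − rho). With d = 0.4:

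| rho (assumed) | ANCOVA, 6 / 15 months | Change score, 6 / 15 months |
|---|---|---|
| 0 | 89.0 / 88.9% | 57.3 / 59.0% |
| 0.1 | 89.3 / 89.2% | 62.6 / 64.0% |
| 0.2 | 90.3 / 90.2% | 68.5 / 69.5% |
| 0.3 | 91.9 / 91.7% | 75.0 / 75.7% |
| 0.5 | 96.2 / 96.0% | 89.0 / 88.9% |

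**5. Repeated-measures model instead of ANCOVA.** By normal approximation with a compound-symmetric covariance, dropout at random and 5–10% assumed lost by Cycle 3, a mixed model for repeated measures (MMRM) adds at most about 0.3 percentage points to ANCOVA at rho 0.3 or 0.5.

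**6. Skewed scores.** A simulation used rounded 0–16 scores with skewness about −1.15 and a 1.0-point shift (both assumed). Under the null, all four tests held their level: 0.8–1.1% against 1.0%, and 1.4–1.6% against 1.5%. Power was:

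| Test | Power |
|---|---|
| t-test | 53–56% |
| Wilcoxon | 75–77% |
| ANCOVA, observed correlation 0.32 | 59–60% |
| Rank ANCOVA, observed correlation 0.32 | 81–82% |
| ANCOVA, observed correlation 0.52 | 68–70% |
| Rank ANCOVA, observed correlation 0.52 | 88–89% |

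Under skew, the adjusted counterpart of Wilcoxon is therefore rank ANCOVA, not ordinary ANCOVA.

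**7. The downside.** The calendar in section 7.1 puts the baseline FBSI at Day 1 of Cycle 1. Section 3.2 allows up to 6 weeks from randomisation to that day, section 9.1 describes the trial as open-label, and section 5.5.2 asks for surveys before the clinician visit only where possible. Suppose knowledge of the arm shifts mean baseline by 0.1 SD (0.1 × 3.7 = 0.37 points, assumed) without affecting later scores. The adjusted estimate then moves by rho × 0.37 points:

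| rho | Estimate moves by | One-sided type I error, platinum lower at baseline (6 / 15 months) | Power, platinum higher at baseline (6 / 15 months) |
|---|---|---|---|
| 0.3 | 0.11 points | 2.03 / 2.85% | 86.8 / 86.8% |
| 0.5 | 0.19 points | 3.49 / 4.64% | 89.6 / 89.6% |

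The nominal levels are 1.0% and 1.5%. With an assumed shift of 0.2 SD, type I error becomes 3.9 / 5.1% at rho 0.3 and 9.7 / 11.7% at rho 0.5. The unadjusted test is unaffected in every case.

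**The case against.** The strongest reply is that nothing is broken. The planned tests are valid, the objective is secondary, and power is already at target within rounding. The gain rests on a correlation the documents do not give, and at 0.1 or 0.2 it is about one percentage point or less. Meanwhile the adjustment introduces a dependence that the t-test does not have: a baseline taken after open-label allocation. The correlation that gives the larger gain also gives the larger inflation if baseline is shifted. Section 7.1 also allows a window of 3 working days either side for procedures not otherwise specified, which on its face could put the survey after the first dose. And the PRO study opened with addendum #4, so a new instruction cannot change baselines already collected.

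Much of this stands. The size of the gain is uncertain, and for patients already surveyed only the recorded survey date and an unadjusted sensitivity analysis offer protection. The 0.1 SD shift is an illustration, not a bound. It is also true that comparing scores at all time points already covers baseline scores by arm, and that rank ANCOVA gives no effect in points to set against the 1.5-point difference.

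It does not remove the case for adjustment. At zero correlation the cost is one degree of freedom. The planned change-score tests depend on the same post-allocation baseline and are weaker than ANCOVA at every correlation examined. The risk can be made visible by reporting the baseline by arm and by survey date, and checked against the unadjusted result.

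**Conclusion.** The point holds as an improvement. The two powered tests leave an available baseline covariate unused. Adjustment would raise power from about 89% to about 90% at correlation 0.2, 92% at 0.3 and 96% at 0.5, at both visits and with no added patients. No shortfall in the current plan is claimed. The conclusion rests on two assumptions: a positive correlation between baseline and follow-up FBSI-TSE, which the documents do not report, and a baseline score not affected by knowledge of the arm. The second is the one to watch, because a modest shift could double or triple the small one-sided error rates. The model and the timing of the baseline survey therefore have to be settled together.

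**What to change.** In section 9.6.2:

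- Name ANCOVA of FBSI-TSE on baseline FBSI-TSE, at each of 6 and 15 months, as the primary test, and attach the existing two-sided 2% and 3% levels to it explicitly.
- Keep the asymmetry rule, with rank ANCOVA (ranks of the score on ranks of baseline) in place of Wilcoxon. An MMRM with categorical visit, arm, arm-by-visit interaction and baseline is an acceptable alternative, with little further gain.
- State how a missing baseline is handled, for example by the baseline mean of both arms pooled.
- Keep the unadjusted t-test or Wilcoxon as a fixed sensitivity analysis.

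In sections 5.5 and 7.1, require the baseline survey before the first dose and preferably before allocation is disclosed, and record its date against randomisation. Report baseline scores by arm.

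The cost is SAP wording and one instruction on survey timing, with no new patients, visits or questionnaire items. For patients already surveyed after allocation the timing cannot be changed, so the dates and the sensitivity analysis must carry the weight.

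### The primary HRQL tests at 6 and 15 months are complete-case tests, with no rule for deaths or missing forms and no missing-data sensitivity analysis, despite 12% and 20% expected loss

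*Combined protocol and SAP*

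**What the plan says.** Section 9.6.1 makes the FBSI treatment side-effect subscale (FBSI-TSE) at 6 and 15 months the two primary PRO endpoints, tested at one-sided 1.0% and 1.5%. Section 9.6.2 gives the test: "The assessment scores for the HRQL will be compared between the two treatment arms at all time points, using two samples t test", or a Wilcoxon rank sum test if the scores are not symmetric. On who is analysed, it says: "Any participants who take the PROs surveys at more than 1 time-point will be eligible for analysis". It then says that the primary HRQL analysis covers all eligible patients.

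Loss is expected. Section 9.6.1 assumes about 12% by 6 months and "20% by 15 months after the start of chemotherapy for the PROs assessment in both arms", and sets enrolment at 362 to allow for it.

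The provisions that bear on missing data are:
- prorating of unanswered items within a returned form, and a descriptive look at missing-data patterns (Section 9.6.2);
- a longitudinal model, with the status "Mixed effect models will be constructed as another exploratory analysis" (Section 9.6.2), in which time is linear or categorical depending on the observed trend;
- recording of the reason for an uncompleted questionnaire (Section 5.5.2);
- continued PRO assessment after recurrence (Section 5.5).

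Footnote 7 to the Section 7.1 calendar says instead that after a recurrence the patient is followed for survival and no other protocol procedures are needed.

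**The concern.** A patient who completes the baseline and cycle 3 surveys and then dies, withdraws or stops returning forms is eligible under Section 9.6.2 but enters neither primary test. Enrolling 362 replaces the lost precision. It does not protect against bias if those who are lost differ from those who stay.

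That is plausible here. Section 1.8 expects platinum to be better tolerated in the short term, and reports that nearly one-fifth of patients in the earlier adjuvant capecitabine trial stopped treatment for adverse events. Loss could therefore follow earlier scores and be unequal between arms.

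HRQL is a named secondary objective (Section 2.2.5). Section 1.8 says tolerability information will matter for counselling, especially if platinum proves non-inferior but not superior. A distorted contrast in either direction would carry into that counselling.

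**Working it through.** **1. The plan's sample size.** Inputs from Section 9.6.1: an MID of 1.5 points and an SD of 3.7; at 6 months, 326 evaluable patients for 90% power with a standardised effect of 0.4 and one-sided alpha 0.01; at the later visit, "290 patients would be needed for this test with one-sided type I error rate of 0.015 and 90% power". Allocation is 1:1 (Section 9.2). Normal approximation, per arm: n = 2(z for alpha + z for power)² / d².
- 6 months, d = 0.40: 2 × (2.326 + 1.282)² / 0.16 = 162.7, so 163 per arm and 326 in total. Reproduced.
- 15 months, d = 1.5/3.7 = 0.405: 2 × (2.170 + 1.282)² / 0.1644 = 145 per arm and 290 in total. Reproduced. The exact t-test power with 290 is 89.8%.
- Attrition: 362 × 0.88 = 319 at 6 months, slightly under 326, with power still about 89%. 362 × 0.80 = 290 at 15 months.

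Precision is therefore adequately covered. About 43 (12%) and 72 (20%) of the 362 would be absent from the two tests.

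**2. Deaths.** The documents assign no share of PRO attrition to death. The only source is the OS assumption for basal-like patients in Section 9.3.1: 5-year OS 66% on capecitabine and 75% on platinum, exponential. Deaths by month t = 1 − S^(t/60).

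| | Capecitabine | Platinum | Mean |
|---|---|---|---|
| 6 months | 1 − 0.66^0.10 = 4.1% | 1 − 0.75^0.10 = 2.8% | 3.5% |
| 15 months | 1 − 0.66^0.25 = 9.9% | 1 − 0.75^0.25 = 6.9% | 8.4% |

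These are indicative only: Section 9.6 enrols the PRO cohort regardless of subtype, and 75% is the superiority alternative.

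**3. Loss that depends on the previous score.** Simulation with 181 per arm, SD 3.7, true difference 1.5 and monotone dropout of 12% by 6 months and 20% by 15 months. Assumed, not from the documents: between-visit correlation 0.5 to 0.7, and dropout log-odds rising 0.7 to 1.2 for each SD that the previous score is lower. The likelihood estimate uses all post-baseline scores and no baseline. Results at 15 months, one-sided 0.015:

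| Setting | t test | Likelihood estimate |
|---|---|---|
| One dropout rule for both arms | 1.33 to 1.44, power 85–89% | 1.49 to 1.51, power 90–94% |
| 20% loss in each arm, same score-dependence | 1.49 to 1.52 | about 1.50 |
| One rule, early difference 1.5, true 15-month difference 0 | −0.06 to −0.18 | about 0 |

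Under one common rule, attrition is about 22–23% on capecitabine and 17–18% on platinum, because capecitabine scores are lower. That imbalance produces the bias. Repeat runs agreed to within simulation error (first row 1.31 to 1.46).

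**4. Loss that depends on the unseen score at the visit.** Assumed means 10.5 and 12, SD 3.7, log-odds 1 per SD, about 20% missing overall. Complete-case difference for a true 1.50:
- unrelated to score: 1.50
- low scores lost by one rule in both arms: 1.34
- low scores lost, 25% capecitabine and 15% platinum: 1.21
- low scores lost, 15% capecitabine and 25% platinum: 1.81
- low scores lost on capecitabine only: 0.86
- low scores lost on platinum only: 2.14

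**The case against.** A reader might infer that the t tests are biased toward no difference. The documents do not support that. Section 9.6.1 states its attrition rates for both arms, and with equal loss the simulated bias vanishes. With a true 15-month difference of zero, the bias under one rule is away from the null, and step 4 gives values on both sides of 1.50. Nor do the documents support saying that about 8% of the loss is death: that figure is derived, fits 15 months only, and comes from basal-like OS assumptions.

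Other objections carry weight:
- The effect under the common rule is modest: 0.06 to 0.17 points, or 4 to 11% of the 1.5-point minimally important difference. Power of 85–89% compares with 89.8% for the plain t test.
- The simulation in step 3 draws dropout from earlier scores, so the likelihood estimate is unbiased by construction. It shows nothing about loss that depends on the unseen score.
- A missing-at-random likelihood model implicitly extrapolates scores past death. In a death-only simulation at the plan's rates, survivors differed by 1.43 to 1.46, which is what the t test estimates, while the model returned 1.49 to 1.51. Calling the model a while-alive estimate would be wrong.
- Patients missing later forms still enter the cycle 3 comparison and the exploratory model, and reasons for missing questionnaires are recorded.

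These points limit the size and direction of the claim. They do not supply a rule for deaths or missing forms in the two primary tests, or a sensitivity analysis. Continued assessment after recurrence is a safeguard only if footnote 7 of Section 7.1 does not override it.

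**Conclusion.** The point holds in a limited form. The two primary HRQL tests are complete-case, leave out patients whom Section 9.6.2 counts as eligible, and have no stated handling of death or missing forms and no missing-data sensitivity analysis, against expected loss of 12% and 20%.

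Bias is possible and its direction is unknown in advance. It is essentially absent if loss is 20% in each arm with the same dependence on earlier scores. It is modest if one rule removes low scorers in both arms. It could be larger, either way, if the arms lose different kinds of patients. The simulated figures rest on the assumed correlations and dropout slopes. The matter concerns a secondary objective, not the primary IDFS analysis, but it is worth correcting because a better analysis is already planned on data already being collected.

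**What to change.** In Section 9.6.2:
- Make the planned mixed model the primary HRQL analysis, with categorical visit, arm-by-visit terms and unstructured covariance fixed in advance in place of the data-driven time coding. Include every PRO patient with at least one post-baseline FBSI-TSE score. Anyone with surveys at more than one time point has at least one post-baseline survey, so this brings the analysis into line with the stated eligibility.
- Test the 6- and 15-month contrasts at the existing one-sided 1.0% and 1.5%. Keep the t or Wilcoxon tests as supportive.
- State that the model assumes missing-at-random given earlier scores and implicitly extrapolates past death. Do not label it a while-alive estimate.
- Report deaths before each visit by arm, and add a sensitivity analysis that ranks deaths worst.

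Section 5.5 and footnote 7 of Section 7.1 must be reconciled on whether PRO forms continue after recurrence.

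The cost is SAP wording and slightly more analysis work; sample size, alpha split and data collection are unchanged. The downside is reliance on missing-at-random given earlier scores. That is weaker than what the completers' test needs to estimate the same contrast, but it cannot be verified from the data.
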